9.9 QUANTIFICATION OF PLASMA BIOMARKERS OF NEUROINFLAMMATION AND DEGRADATION

Through a collaboration with [name] and [name] at the Clinical Neurochemistry Lab, University of Gothenburg, Sweden, we will quantify plasma levels of neurofilament light chain (NFL), p-tau and t-tau. We will assess longitudinal changes in the level of these biomarkers and will also compare against biomarker levels in other cohorts of HIV-infected individuals.

9.10 PLASMA CYTOKINES, CHEMOKINES AND GENE PRODUCTS

We will quantify levels of plasma cytokines and chemokines and selected products of differentially expressed genes. The latter will be based on our bioinformatic analysis of gene expression levels as explained in subsection 9.8. This will be done using commercially available ELISA kits and Luminex multiplexing to quantify a broad panel of cytokines in plasma.

9.11 HISTONE ACETYLATION AND pTEFB AND NFkB ACTIVATION

Through a collaboration with [name] at Case Western University, USA, we will assess markers of cellular function relevant to latency reversal. We will apply samples from the study to several newly developed assays, which includes H3K9 histone acetylation, pTEFB activation and NFkB activation.

9.12 EFFECTS OF VORINOSTAT AND DISULFIRAM ON ASTROCYTES

To determine the effect of the transcriptome of vorinostat and or disulfiram in cells from the central nervous system and peripheral blood mononuclear cells we intend to perform RNA

sequencing on primary astrocytes, astrocyte cell lines and PBMCs. These different cells will be exposed to C_{max} drug levels that were observed in the trial. We will determine H3K9 histone acetylation, pTEFB activation and NFkB activation in these cells and determine differential gene expression compared to untreated cells. We will perform bulk RNA sequencing by extracting RNA from 2 million treated cells per condition and perform 3'-end poly A paired ended 2x100bp sequencing using the Illumina Miseq platform. We expect that the epigenetic markers in these different cell types will react differently to these LRAs.

10. PARTICIPANT SAFETY AND WITHDRAWAL

10.1 DEFINITIONS

10.1.1 Adverse Events (AE)

An AE is any untoward medical occurrence in a patient or clinical investigation participant administered a pharmaceutical product that does not necessarily have a causal relationship with this treatment. An AE can therefore be any unfavourable and unintended sign (including an abnormal laboratory finding – see below), symptom, or disease temporally associated with the use of the investigational drug, whether or not causally linked to the investigational drug.

An abnormal laboratory value or test result constitutes an adverse event only if

- It is associated with clinical signs or symptoms
- It leads to a change in study drug dosing or discontinuation from the study
- It requires additional diagnostic testing or medical/surgical intervention
- It is considered to be an adverse event by the investigator

In addition, all cases of drug-drug interaction, pregnancy (with or without outcome), paternal exposure, lactation, overdose, drug abuse and misuse, drug maladministration or accidental exposure and dispensing errors are collected and data based even if no adverse event has been reported.

All adverse events will be reported in accordance with the principles of Good Clinical Practice and the latest requirements of the Medicines for Human Use (Clinical Trials) Regulations.

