Disulfiram and vorinostat have both been shown to increase HIV transcription in vitro¹⁴⁻¹⁶ and in clinical trials^{2,6,17}. With its long-standing use to treat alcoholism, favourable tolerability and lack of mutagenic potential, disulfiram can be administered for extended periods. Vorinostat (Zolinza®), is a pan HDAC inhibitor¹⁸ with regulatory approval for the treatment of cutaneous T cell lymphoma. Although less potent than the more recently licensed HDACi panobinostat and romidepsin, vorinostat has the advantage of being orally administered and has an extensive safety profile. In vitro, compared to other HDACi, vorinostat had minimal effects on suppressing HIV-specific T-cell function, in contrast to romidepsin which potently suppressed T-cell function¹⁹. Finally, we previously showed that vorinostat has acceptable tolerability during daily dosing for 14 days, which led to increases in HIV transcription in ART-suppressed HIV patients in blood and in rectal tissue and no adverse effects on HIV-specific T-cells in vivo². In addition, long term follow up of these participants for two years demonstrated no adverse clinical or virological effects of vorinostat in HIV-infected individuals on ART [Mota, submitted].

Here we propose to administer disulfiram at 2g/day for 28 days with two additional short courses of vorinostat. The rationale here is to give an LRA for a prolonged period alone and in combination. Disulfiram is the only LRA that has an appropriate toxicity profile, which would allow for prolonged administration. Based on our experience with two clinical studies of disulfiram in HIV infection given at standard dose (500mg/day) for 14 days⁵ and at high dose

(1 and 2 g/day) for 3 days⁶, we believe that administration at 2g/day for 28 days is safe and feasible. Previously, disulfiram was used in the clinical setting at relatively high doses ranging from 1-3 g²⁰ and up to 6g²¹ in individuals with alcoholism, and was generally reported to be safe with the most significant safety concern being fatal disulfiram-induced hepatitis, which is estimated to occur extremely rarely at 1 per 25,000 patients treated/year²⁰.

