4.3.2 Secondary endpoints

- Tolerability as measured by the incidence and severity of adverse events
- Plasma HIV RNA relative to baseline at additional time points
- HIV transcription measured by cell-associated unspliced HIV RNA (CA-US HIV RNA) in peripheral blood CD4+ T cells relative to baseline
- Cell-associated total and integrated HIV DNA in peripheral blood CD4+ T cells relative to baseline
- The frequency of inducible virus as measured by Tat/rev limiting dilution assay (TILDA) in peripheral blood CD4+ T cells relative to baseline
- Concentrations of vorinostat and disulfiram (including its metabolites) in plasma
- p24 expression in CD4+ T-cells relative to baseline

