10.2 RECORDING OF ADVERSE EVENTS

At each contact with the study participant, as indicated in the schedule of activities, information on adverse events is sought by specific questioning and, as appropriate, by examination. Information on all adverse events should be recorded immediately in the source document, and also in the appropriate adverse event module of the CRF. All clearly related signs, symptoms, and abnormal diagnostic procedures results should be recorded in the source document, though they should be grouped under one diagnosis.

All adverse events occurring during the study period - from the time the study participant signs consent (visit 1) to End of study (visit 9) - must be recorded. The clinical course of each event should be followed until resolution, stabilization, or until it has been determined that the study treatment or participation is not the cause. Serious adverse events that are still on-going at the End of Study must be followed up to determine the final outcome. Any serious adverse event that occurs after the study period and is considered to be possibly related to the study treatment or study participation should be recorded and reported immediately.

All AEs must be graded according to the Division of AIDS Table for Grading the Severity of Adult and Pediatric Adverse Events, Version 2, November 2014 and recorded in source notes as well as the AE eCRF with the following information:

- The severity grade (see below)
- Its relationship to the study drugs (suspected/not suspected)
- Its duration (start and end dates or if continuing at study visit)
- Whether it constitutes a serious adverse event (SAE)

All adverse events will be graded in the following manner:

- Grade 1 (Mild): Events require minimal or no treatment and do not interfere with the participant's daily activities.
- Grade 2 (Moderate): Events result in a low level of inconvenience or concern. Moderate events may cause some interference with functioning.
- Grade 3 (Severe): Events interrupt a participant's usual daily activity and may require systemic drug therapy or other treatment. Severe events are usually incapacitating.
- Grade 4 (Life-threatening): Any adverse drug experience that places the participant, in the view of the investigator, at immediate risk of death from the reaction as it occurred (i.e., it does not include a reaction that had it occurred in a more severe form, might have caused death).
- Grade 5 (Death)

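### Tolerability is analysed from adverse events only, so asymptomatic laboratory changes that nobody acts on can be left out of it

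*Combined protocol and SAP*

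**What the plan says.** - **Objective.** The synopsis and section 4.2.2 make tolerability a primary objective.
- **Endpoint.** Section 4.3.2 places it among the secondary endpoints: "Tolerability as measured by the incidence and severity of adverse events". Section 9.2 describes the assessment in the same terms.
- **Analysis.** Section 11.2 summarises AEs and SAEs by severity and causality, with numbers of events and numbers and percentages of participants. It is descriptive, with no formal comparison. No laboratory summary is named.
- **AE definition.** Section 10.1.1 opens its laboratory rule with "An abnormal laboratory value or test result constitutes an adverse event only if" and lists four conditions. In brief, the first is symptoms or signs, the second is altered dosing or leaving the study, and the third is a need for more tests or for treatment. The fourth is discretionary: "It is considered to be an adverse event by the investigator". None refers to a grade or a multiple of a normal limit.
- **Grading.** Section 10.2 requires every AE to be graded by the Division of AIDS table. It then says that all AEs will be graded by a five-level list worded mainly in terms of function and treatment. Grade 1 there begins "Events require minimal or no treatment and do not interfere with" and goes on to name everyday activity.
- **Collection.** Table 1 schedules haematology and chemistry at screening, Days 8, 11, 22 and 28, and Day 196. There is no safety panel at Visit 2 (baseline).
- **Known risks.** Section 3.3 describes past high-dose use of disulfiram as generally safe, "the most significant safety concern being fatal disulfiram-induced hepatitis", and puts that event at 1 per 25,000 patients treated per year. Section 13.4.2 lists dose-related anaemia and thrombocytopenia with vorinostat.

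**The concern.** The plan collects the laboratory data that bear on the liver and blood-count risks it names, but its analysis sees those data only after they pass through the AE definition. Whether a given value passes depends on symptoms, on someone acting, or on judgement in an open-label, single-arm study. Two participants with the same transaminase rise could be handled differently, and a reader of the AE table could not tell.

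The regimen makes this matter more. Section 3.3 cites HIV experience with disulfiram at 2 g/day for 3 days, whereas this trial gives it for 28 days. Section 3.3 also describes the trial as the first combination study of this kind in people on ART. With no control arm, change within participant is the only comparison available for laboratory safety, and it is not planned.

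**Working it through.** No figure in the documents is in dispute. The check sets the sections side by side and follows a laboratory value through them.

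**1. Reading the four conditions.** The list in section 10.1.1 has no 'and' or 'or'. It is read here as any one of the four, which is the reading most favourable to the plan.

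**2. Following an asymptomatic value found on Day 28.** Section 8.8 places this visit after the last disulfiram dose, and vorinostat ended on Day 24.
- Symptoms: none, by assumption.
- Dosing change: no study dosing remains to change. Discontinuation from the study remains possible.
- Further testing or intervention: met only if someone orders it. The next scheduled safety panel is Day 196; Table 1 has none at Day 56.
- Investigator's judgement: met only if the investigator so decides.

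If no one acts on the value or calls it an AE, it is not an AE. It then does not receive the grade that section 10.2 requires of AEs, and it does not appear in the section 11.2 summary.

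**3. Looking for another route into the results.** Section 5.5 makes laboratory printouts source data, so the values are kept, but it plans no table. Section 8.2 says that new findings after consent are to be recorded as AEs. That sentence sits in the screening physical-examination item, does not mention laboratory values, and does not displace the specific rule in section 10.1.1. Section 11.3 covers gene expression and biomarkers, not safety panels. No section closes the gap.

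**4. Grading a laboratory value that is recorded as an AE.** Both rules in section 10.2 are mandatory. The functional list has no laboratory cut-offs, so an untreated value that does not affect daily activities fits its Grade 1 wording. The protocol does not reproduce the Division of AIDS table. Assuming that it grades laboratory values by magnitude, the same value can receive a higher grade there. Section 10.2 does not say which prevails.

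**5. What can be counted.** Scheduled post-dose panels: 15 × 5 = 75. Of these, 15 × 4 = 60 fall between Day 8 and Day 28, and 15 fall at Day 196, which is 196 − 28 = 168 days after the last disulfiram dose. This counts panels without a planned summary, not abnormal or lost values.

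**6. Illustration with assumed rates.** Let p be the true proportion of participants with an asymptomatic laboratory toxicity and q the share of those recorded as AEs. The chance that the AE table shows at least one case among 15 is 1 − (1 − pq)^15. Neither p nor q is in the documents.

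| p | q = 100% | q = 50% | q = 25% |
|---|---|---|---|
| 5% | 0.537 | 0.316 | 0.172 |
| 10% | 0.794 | 0.537 | 0.316 |
| 20% | 0.965 | 0.794 | 0.537 |

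For example, with p = 10% and q = 50%: 1 − 0.95^15 = 0.537.

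**7. An example inside the documents.** Section 13.4.2 reports raised glucose on laboratory testing in 60/87 = 69% of vorinostat-treated lymphoma patients, against hyperglycaemia as a drug-related adverse experience in 4/86 = 4.7%. The contrast is imperfect: only 5 of the rises were Grade 3, the second figure is limited to drug-related events, and glucose is not in this trial's listed panel. It shows only that laboratory findings and AE reports can differ widely for one of the two drugs.

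**The case against.** The strongest reply is that the exposed part is narrow. A repeat test, a dosing change or the investigator's view each makes a value an AE without symptoms. Section 13.4.2 links reduced platelets or haemoglobin on vorinostat to dose modification or discontinuation, and acting on that would bring the value in. Marked abnormalities will often reach the AE table by one of these routes. This stands. A reader might infer that silent toxicity will be omitted; the documents support only that it can be.

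A reader might also infer from section 10.2 that the functional list makes any symptom-free, untreated value Grade 1 whatever its size. That is wrong. Grade 2 mentions a low level of concern, and Grade 4 rests on the investigator's view of immediate risk of death. What stands is that the two scales can disagree.

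Third, the endpoint is listed as secondary and its analysis is descriptive, so no test or decision rule depends on the count. This also stands: the gap affects how the tolerability objective is answered, not the primary endpoint.

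Fourth, it is tempting to size the problem by 1/15 = 6.7 percentage points per participant, or by the exact 95% upper limit for 0/15, 1 − 0.025^(1/15) = 21.8%. Both follow from the sample size under any AE definition, and the fix changes neither, so they do not measure this defect.

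Finally, the named risks carry qualifiers. Section 3.3 calls fatal hepatitis extremely rare, and section 13.4.2 says that the blood-count effects are more common above 400 mg per day, whereas this trial uses 400 mg on six days. These lower the expected frequency. They do not explain why panels collected for safety have no planned summary.

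**Conclusion.** The point holds in limited form. Sections 4.3.2, 9.2, 10.1.1 and 11.2, followed as written, allow asymptomatic liver-enzyme or blood-count changes that are not acted on, and not judged to be AEs, to be absent from the answer to a primary objective. Section 10.2 can also give different severities for the same asymptomatic laboratory AE.

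The gap is in classification and reporting, not in collection. Its size cannot be estimated from the documents; the table of probabilities depends wholly on assumed p and q. The conclusion rests on reading the four conditions as alternatives. The grading part also assumes that the Division of AIDS table grades laboratory values by magnitude. The primary efficacy comparison is unaffected. This should be corrected before the safety analysis, because the data already exist and the remedy is small.

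**What to change.** **Section 11.2.** Add, for all dosed participants, a descriptive table of ALT, AST, bilirubin, creatinine/eGFR, haemoglobin, platelets and neutrophils. For each, show the worst post-dose Division of AIDS grade and the shift from the last pre-dose (screening) value, whether or not the result was recorded as an AE. The shift matters because section 6.3 admits participants with transaminases above normal but below 3 × ULN.

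**Section 10.2.** State that laboratory values are graded by the Division of AIDS table. The AE definition in section 10.1.1 can stay as it is.

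**Cost.** One table from data already scheduled and one sentence; no new visits, blood draws or change in clinical management. The limitation is the reference value. Because Visit 2 has no safety panel, it may be up to 42 days old, or 84 days where section 8.2 accepts standard-of-care results. The table should report its age. The synopsis gives 3 weeks and section 6.3 gives 6 weeks for the eligibility laboratory values, and these should be reconciled with section 8.2.

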10.1.2 Serious Adverse Events (SAEs)

A SAE is any untoward medical occurrence that at any dose:

- Results in death
- Is life-threatening
- Results in persistent or significant disability/incapacity
- Constitutes a congenital anomaly/birth defect
- Requires inpatient hospitalization or prolongation of existing hospitalization, *unless hospitalization is for:*
 - Routine treatment or monitoring of the studied indication, not associated with any deterioration in condition
 - Elective or pre-planned treatment for a pre-existing condition that is unrelated to the indication under study and has not worsened since the start of the study drug

- Treatment on an emergency outpatient basis for an event not fulfilling any of the definitions of a SAE given above and not resulting in hospital admission
- Social reasons and respite care in the absence of any deterioration in the patient's general condition
- Is medically significant, i.e. defined as an event that jeopardizes the patient or may require medical or surgical intervention to prevent one of the outcomes listed above

Unlike routine safety assessments, SAEs are monitored continuously and have special reporting.

10.1.3 Pregnancy

Any female study participant who becomes pregnant during the study must be immediately withdrawn from study drugs to eliminate further exposure to the embryo/foetus.

Any pregnancy that occurs during study participation is to be reported on a specific pregnancy site worksheet and SAE form. To ensure participant safety, each pregnancy must be reported to Sponsor within one week of learning of its occurrence. The pregnancy must be followed up to determine outcome (including premature termination) and status of mother and child, which must also be reported to Sponsor using designated data collection forms. Pregnancy complications and elective terminations for medical reasons must be reported as an AE or SAE. Spontaneous abortions must be reported as an SAE.

Any SAE occurring in association with a pregnancy brought to the investigator's attention after the subject has completed the study and considered by the investigator as possibly related to the investigational product, must be promptly reported to Sponsor.

10.2 RECORDING OF ADVERSE EVENTS

At each contact with the study participant, as indicated in the schedule of activities, information on adverse events is sought by specific questioning and, as appropriate, by examination. Information on all adverse events should be recorded immediately in the source document, and also in the appropriate adverse event module of the CRF. All clearly related signs, symptoms, and abnormal diagnostic procedures results should be recorded in the source document, though they should be grouped under one diagnosis.

All adverse events occurring during the study period - from the time the study participant signs consent (visit 1) to End of study (visit 9) - must be recorded. The clinical course of each event should be followed until resolution, stabilization, or until it has been determined that the study treatment or participation is not the cause. Serious adverse events that are still on-going at the End of Study must be followed up to determine the final outcome. Any serious adverse event that occurs after the study period and is considered to be possibly related to the study treatment or study participation should be recorded and reported immediately.

All AEs must be graded according to the Division of AIDS Table for Grading the Severity of Adult and Pediatric Adverse Events, Version 2, November 2014 and recorded in source notes as well as the AE eCRF with the following information:

- The severity grade (see below)
- Its relationship to the study drugs (suspected/not suspected)
- Its duration (start and end dates or if continuing at study visit)
- Whether it constitutes a serious adverse event (SAE)

All adverse events will be graded in the following manner:

- Grade 1 (Mild): Events require minimal or no treatment and do not interfere with the participant's daily activities.
- Grade 2 (Moderate): Events result in a low level of inconvenience or concern. Moderate events may cause some interference with functioning.
- Grade 3 (Severe): Events interrupt a participant's usual daily activity and may require systemic drug therapy or other treatment. Severe events are usually incapacitating.
- Grade 4 (Life-threatening): Any adverse drug experience that places the participant, in the view of the investigator, at immediate risk of death from the reaction as it occurred (i.e., it does not include a reaction that had it occurred in a more severe form, might have caused death).
- Grade 5 (Death)

10.3 REPORTING OF SERIOUS ADVERSE EVENTS

SAEs will be noted in source documentation. Information about all SAEs should be recorded on a Serious Adverse Event Report Form. The investigator must inform the sponsor, principal investigator and HREC, assess the relationship to study drug, complete an SAE Report Form, and send the signed form by fax within 24 hours of notification of the SAE to Merck Global Safety and HREC.

The original copy of the SAE Report Form and the fax confirmation sheet or email confirmation must be maintained at the study site.

10.4 SUSPECTED UNEXPECTED SERIOUS ADVERSE REACTIONS (SUSARS)

If the SAE is not previously documented in the product information or package insert (new occurrence) and is thought related to the study drug, it qualifies as a SUSAR. A sponsor associate may require further information from the investigator for Health Authority reporting.

The minimum necessary information to be provided at the time of the initial report includes:

- An identifiable patient
- An identifiable medicinal and/or pharmaceutical product
- An identifiable reporter
- A serious adverse event

